9.1.1. Relationship to Study Drug

Adverse events will be classified as “related” to study treatment if the relationship was rated by the investigator as possibly related or probably related. Adverse events related to any study drug component (relugolix or placebo and E2/NETA or placebo) will be considered as related to study drug.

9.1.2. Severity of Adverse Event

Grade 3 or higher adverse events will be summarized by SOC, PT, and/or maximum severity, relationship to study treatment.

9.1.3. Serious Adverse Event

Serious adverse events will be summarized by SOC, PT, and/or maximum severity, relationship to study treatment.

The data handling conventions for and the definition of a serious adverse event are discussed in this section. All deaths during the study, including the post treatment follow-up period, and deaths that resulted from a process that began during the study, should be included in the analysis. For more details, deaths occurring during the following time periods or under the following conditions should be considered:

- Deaths occurring during participation in this randomized withdrawal study;
- Deaths occurring after a patient leaves the study, or otherwise discontinues study drug, whether or not the patient completes the study to the nominal endpoint, if the death:
 - Is the result of a process initiated during the study or other drug exposure, regardless of when it actually occurs; or
 - Occurs within a time period that might reflect drug toxicity for a patient leaving a study or otherwise discontinuing drug.

9.1.4. Adverse Event Leading to Withdrawal of Study Drug

Adverse events leading to withdrawal of study drug are those adverse events collected from the adverse event eCRF pages with “drug withdrawn” as the action taken with study drug.

Adverse events with “drug withdrawn” as action taken due to any one of the components of study drug will be considered as leading to withdrawal of study drug.

9.1.5. Adverse Events Leading to Dose Interruption

Adverse events leading to dose interruption are those adverse events collected from the adverse event eCRF pages with “drug interrupted” as their action taken with study drug.

Adverse events with “drug interrupted” as action taken due to any one of the components of study drug will be considered as leading to dose interruption.

9.1.6. Adverse Events Resulting to Fatal Outcome

Adverse events resulting in a fatal outcome are those adverse events collected from the adverse event eCRF pages with “fatal” as their outcome.

The fatal events, if any, will be provided in a by-subject listing.

9.1.7. Other Safety Parameters of Interest

In addition, other safety parameters of interest defined in [Table 15](#) summarized by decreasing frequency of PT under each safety population.

Table 15: Other Safety Parameters of Interest

Category	Search Criteria
Bone health related events	Osteoporosis/Osteopenia SMQ (broad) Fracture (custom SMQ): All preferred terms including the term “fracture,” excluding “Tooth fracture” and “Fracture of penis”
Hepatic transaminase elevations	Drug-related hepatic disorders – comprehensive SMQ (narrow)
Carbohydrate and lipid metabolic effects	Dyslipidemia SMQ Hyperglycemia/new onset diabetes mellitus SMQ (narrow)
Vasomotor symptoms	The following five Preferred Terms will be included: 
 • Hyperhidrosis; • Feeling hot; • Hot flush; • Night sweats; • Flushing.
Mood disorders	MedDRA Depression and Suicide/Self-Injury SMQ (broad)

Abbreviations: MedDRA = Medical Dictionary for Regulatory Activities; SMQ = Standardized MedDRA Query.

9.1.8. Adverse Events of Clinical Interest

Adverse Events of clinical interest in the randomized withdraw study are defined as any increase in ALT or AST $\geq 3 \times$ ULN, which are reported as “Yes” for adverse events of clinical interest in the adverse event CRF. Adverse events of clinical interest will be summarized.

9.2. Laboratory Data

Laboratory parameters, including chemistry and hematology panels, specified as per protocol for the randomized withdrawal study, and collected from the central laboratory will be tabulated and presented in by-patient listings. Local laboratory parameters will not be used for summary. Urinalysis and hepatitis virus serological test results will be provided in by-patient listing only.

The National Cancer Institute CTCAE Grading Scale with numeric component will be used to categorize toxicity grade for laboratory parameters (CTCAE v5.0, dated 27 Nov 2017). Parameters that have criteria available for both low and high values (eg, hypercalcemia for a high value of calcium and hypocalcemia for a low value of calcium) will be summarized for both criteria (low and high). Patients will only be counted once for each criterion. The same patient can be counted for both criteria if she has laboratory values meeting each criterion. Shift tables will be provided for each parameter, which is gradable by the CTCAE, to summarize Week 52/Baseline toxicity grade versus worst post-Baseline toxicity grade during this randomized withdrawal study. For laboratory parameters that are not gradable by the CTCAE, a shift table based upon the normal range (low, normal, and high) will be provided for each parameter to summarize the Week 52/Baseline versus worst post-Baseline results during this randomized withdrawal study. A shift table for selected parameters based on predefined

categories (refer to [Appendix 1](#)) will be provided to summarize Week 52/Baseline category versus post-baseline category in the randomized withdrawal study. The parameters include glucose, fasting glucose, HbA1c, low density cholesterol, and high-density cholesterol.

Boxplots of laboratory values over time in the randomized withdrawal study, will be plotted for key laboratory parameters. These laboratory parameters include, but are not limited to, hematology (hemoglobin, platelets, leukocytes, neutrophils), creatinine, glomerular filtration rate, and hepatic function panel (alanine aminotransferase [ALT], aspartate aminotransferase [AST], alkaline phosphatase [ALP], and total bilirubin).

The change from Week 52/Baseline to each post-Baseline study visit will be presented by treatment group for each laboratory test in both tables and figures.

The number and proportion of patients with liver test elevations will be presented by treatment group. Liver test elevations are assessed by using post-Baseline results for ALT, AST, ALP, and total bilirubin based on the definitions presented in [Table 16](#).

Table 16: Categories of Liver Test Elevations

Laboratory Test	Category
ALT or AST	ALT or AST > ULN < 3 × ULN ALT or AST ≥ 3 × to < 5 × ULN ALT or AST ≥ 5 × to < 10 × ULN ALT or AST ≥ 10 to < 20 × ULN ALT or AST ≥ 20 × ULN
Total bilirubin	Total bilirubin > 2 × ULN
ALT or AST and total bilirubin	ALT or AST ≥ 3 × ULN + total bilirubin > 2 × ULN
ALT or AST, total bilirubin, and ALP	ALT or AST ≥ 3 x ULN + total bilirubin > 2 × ULN + ALP < 2 × ULN

Abbreviations: ALP = alkaline phosphatase; ALT = alanine aminotransferase; AST = aspartate aminotransferase; ULN = upper limit of normal.

The number and percentage of patients with concurrent (defined as measurements on the same day) ALT or AST ≥ 3 × ULN and total bilirubin > 2 × ULN will also be presented.

Selected chemistry and hematology test results meeting pre-defined limits of change at any time and based on last observation on treatment will be also summarized per pre-defined threshold (refer to [Appendix 2](#)) by treatment group.

9.3. Other Safety Analyses

9.3.1. Electrocardiograms

ECG was collected at unscheduled visit only besides at Week 52 (which was collected as part of the LTE study). Overall ECG assessments will be listed.

9.3.2. Vital Signs and Body Weight

Blood pressure (systolic and diastolic), heart rate, weight, and BMI will be summarized at Week 52/Baseline and each subsequent scheduled assessment by treatment group. Change from Week 52/Baseline will be calculated and presented for each parameter at all scheduled post-Baseline assessment time points in both tables and figures. All vital sign data will also be provided in by-patient listings.

Potentially clinically significant abnormalities in vital signs are defined in [Table 17](#), and they will be summarized by using post-Baseline values that meet the defined criteria. Potentially clinically significant abnormalities will also be flagged in by-patient listings.

Table 17: Categories of Potentially Clinically Significant Abnormalities in Vital Signs

Parameter	Category
Systolic blood pressure	≥ 140 mmHg and greater than Week 52/Baseline
	≥ 180 mmHg and greater than Week 52/Baseline
	≤ 90 mmHg and less than Week 52/Baseline
	Increase of ≥ 20 mmHg from Week 52/Baseline Decrease of ≥ 20 mmHg from Week 52/Baseline
Diastolic blood pressure	≥ 90 mmHg and greater than Week 52/Baseline
	≥ 105 mmHg and greater than Week 52/Baseline
	≤ 50 mmHg and less than Week 52/Baseline
	Increase of ≥ 15 mmHg from Week 52/Baseline Decrease of ≥ 15 mmHg from Week 52/Baseline
Heart rate	≥ 120 bpm and greater than Week 52/Baseline
	< 45 bpm and less than Week 52/Baseline
	Increase of ≥ 15 bpm from Week 52/Baseline
	Decrease of ≥ 15 bpm from Week 52/Baseline

Abbreviations: bpm = beats per minute; mmHg = millimeters of mercury.

Potentially clinically significant abnormalities in post-Baseline weight are to be summarized using the categories specified in [Table 18](#). Potentially clinically significant abnormalities in weight will also be flagged in by-patient listings.

Table 18: Categories of Potentially Clinically Significant Abnormalities in Weight

Parameter	Category
Body weight	Increase of $\geq 5\%$ from Week 52/Baseline
	Increase of $\geq 10\%$ from Week 52/Baseline
	Decrease of $\geq 5\%$ from Week 52/Baseline
	Decrease of $\geq 10\%$ from Week 52/Baseline

9.3.3. Bone Mineral Density

Corrected BMD data will be used for analysis as determined by the central radiology laboratory in the three prespecified anatomical locations: lumbar spine (L1–L4), total hip, and femoral neck.

9.3.3.1. Analysis Using Week 52/Baseline Bone Mineral Density as Baseline

As defined in Section 4.3.6, the BMD at Week 52 of the extension study will be used as the Week 52/Baseline in the randomized withdrawal study as long as it was within 30 days of the first dose date of the randomized study drug. If there are multiple BMD measurements at Week 52 in the extension study, the one closest to the first dose date of the study drug will be used as Week 52/Baseline in the randomized withdrawal study.

BMD at Week 52/Baseline and Week 104 visit will be summarized descriptively by treatment group and each measured anatomical location for all patients in the safety population. Percentage changes from Week 52/Baseline along with 95% CIs of mean percentage changes also will be summarized by treatment group and anatomical location. Mean percentage change from Week 52/Baseline with its corresponding 95% CI will be plotted by visit, treatment group, and anatomical location.

An analysis of covariance (ANCOVA) model will be used to assess BMD at Week 104. The model will include treatment, stratification factors (menstrual blood loss volume at pivotal study baseline, and duration of relugolix exposure prior to randomization), race (African American versus Other) as fixed factors, and age at Week 52/Baseline, Week 52/Baseline BMD value, and BMI at Week 52/Baseline as covariates. Least square means on each anatomical location will be presented and plotted with associated 95% CIs. Taking into consideration of the BMD data collected for patients who prematurely discontinued prior to Week 104, the ANCOVA model analysis will also be performed similarly to assess BMD at Week 104/EOT.

Categorical representation of percentage change from Week 52/Baseline to Week 104 (also Week 104/EOT) will be presented by the number and proportion of patients who had BMD increase $> 0\%$, no change (0%), declines of $\leq 2\%$, $>2\%$ to 3% , $> 3\%$ to 5% , $> 5\%$ to 8% , and $> 8\%$ by pivotal study treatment group and anatomical location. The 95% CIs will be provided for the respective proportions.

Categorical changes from Week 52/Baseline in overall BMD (defined as lumbar spine and total hip) also will be assessed. Femoral neck evaluates a smaller area of bone mass than the total hip and is prone to lower precision in the measurement (Leslie et al. 2007; ISCD 2015). Since

femoral neck BMD may be associated with discordant readings compared with the total hip or lumbar spine due to technical considerations, it is not expected to add meaningful interpretation of overall BMD changes in response to treatment, though will be included for completeness.

Corrected BMD Z-scores and its change from Week 52/Baseline will be summarized by treatment group, visit, and anatomical location with descriptive statistics including 95% CIs, and the number and percentage of patients with a corrected BMD Z-score < -2.0 will be presented by treatment group, visit, and anatomical location. Additionally, categorical change from Week 52/Baseline in Z-score will be summarized as ≥ 0 , < 0 to -0.25 , < -0.25 to -0.5 , < -0.5 to -0.75 , < -0.75 to -1 , < -1 to -2 and < -2 , by treatment group, visit and anatomical location.

BMD percentage changes from Week 52/Baseline will also be summarized by intrinsic factors (eg, age, race, body mass index) and extrinsic factors (eg, geographic region). Subgroups will include, but will not be limited to, the subgroups outlined in [Table 19](#).

Table 19: Planned Subgroup Analyses for Bone Mineral Density

Subgroup Name	Subgroup Level
Geographic region	North America, Other
Age category (years) at pivotal study baseline	< 40 , ≥ 40
Race	Black or African American, Other
Ethnicity	Hispanic or Latino, Not Hispanic or Latino
BMI (kg/m^2) at pivotal study baseline	< 30 , ≥ 30
Duration of exposure to relugolix prior to randomization (weeks)	28, 52

Abbreviations: BMI = body mass index.

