5.3. Randomization and Stratification

Patients are randomized 1:1 ratio to blinded treatment with oral relugolix with E2/NETA (relugolix with add-back) or placebo. Stratification factors for randomization are as follows:

- Baseline MBL volume in the Parent study ($< 225 \text{ mL vs} \ge 225 \text{ mL}$)
- Geographic region (North America vs Europe vs Latin America vs Rest of World)
- Duration of exposure to relugolix (28 weeks vs 52 weeks).

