9.3.3.2. Analysis Using the Pivotal Study Baseline Bone Mineral Density as Baseline

For the visits in pivotal and extension studies, the visit window specified in the extension study SAP Table 3 will be used where the first dose of pivotal study drug was used as the reference.

Percentage changes from pivotal study baseline along with 95% CIs of mean percentage changes since first dose of the pivotal study drug at all the timepoints when BMD was scheduled to be collected in a pivotal study, extension study and the randomized withdrawal study also will be summarized by treatment group and anatomical location. Mean percentage change from pivotal study baseline with its corresponding 95% CI will be plotted by visit, treatment group, and anatomical location.

Categorical representation of percentage change from pivotal study baseline to all the timepoints where BMD was scheduled to be collected since pivotal study baseline will be presented by the number and proportion of patients who had BMD increase $> 0\%$, no change (0%), declines of $\leq 2\%$, $> 2\%$ to 3% , $> 3\%$ to 5% , $> 5\%$ to 8% , and $> 8\%$ by treatment group and anatomical location. The 95% CIs will be provided for the respective proportions.

Categorical changes from pivotal baseline in overall BMD (defined as lumbar spine and total hip) also will be assessed at all the timepoints where BMD was scheduled to be collected since pivotal study baseline.

Corrected BMD Z-scores and its change from pivotal study baseline will be summarized by treatment group, visit, and anatomical location with descriptive statistics including 95% CIs, and the number and percentage of patients with a corrected BMD Z-score < -2.0 will be presented by treatment group, visit, and anatomical location. Additionally, categorical change from pivotal study baseline in Z-score will be summarized as ≥ 0 , < 0 to -0.25 , < -0.25 to -0.5 , < -0.5 to -0.75 , < -0.75 to -1 , < -1 to -2 and < -2 , by treatment group, visit and anatomical location.

These analyses will be carried out by six combined analysis groups where the pivotal study treatment group, LTE study treatment and the randomized withdrawal study treatment group are considered (see the [Table 20](#) below).

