In addition, to observe the long-term impact of relugolix + delayed E2/NETA on BMD loss, these analyses will be performed by the relugolix monotherapy status groups: patients who were previously treated with any relugolix + delayed E2/NETA (from Groups 3 and 4) and the rest of the patients (from Groups 1, 2, 5 and 6).

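### The Week 104 bone density ANCOVA omits pivotal-baseline BMD and the concurrent versus delayed E2/NETA split, passing up a modest precision gain that costs almost nothing

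*SAP*

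**What the plan says.** SAP 9.3.3.1 sets out the whole model. It begins "The model will include treatment, stratification factors (menstrual blood loss volume at pivotal study baseline, and duration of relugolix exposure prior to randomization", and goes on with "race (African American versus Other) as fixed factors, and age at Week 52/Baseline, Week 52/Baseline BMD value, and BMI at Week 52/Baseline as covariates". The same model is repeated for Week 104/EOT. The Week 52 value is a single scan: where there are several, "the one closest to the first dose date of the study drug will be used as Week 52/Baseline". The stated output is "Least square means on each anatomical location will be presented and plotted with associated 95% CIs"; no difference between treatment groups is named.

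The earlier bone history is used in other places, for description only. SAP 9.3.3.2 gives "Percentage changes from pivotal study baseline along with 95% CIs of mean percentage changes since first dose of the pivotal study drug", by the six combined groups of Table 20 and again for "patients who were previously treated with any relugolix + delayed E2/NETA (from Groups 3 and 4") against all others. SAP 9.3.3.3 repeats this from the pivotal Week 12 scan.

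The only element of treatment history in the randomization is "Duration of exposure to relugolix (28 weeks vs 52 weeks"), in Protocol 5.3. The protocol synopsis names percent change in BMD from Week 52 to Week 104 as a safety endpoint and promises its mean and 95% CI for each group.

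**The concern.** When women differ in BMD far more than one scan's measurement error, the ANCOVA slope on the Week 52 scan is close to 1. Error in that scan then passes almost whole into the estimated later change. A second pre-randomization scan at the same site helps to tell a real level from an unusually high or low reading, and this scan is already in the database.

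The 52-week exposure level also pools women who had E2/NETA from the start (Table 20, Groups 1 and 2) with women who had it delayed (Groups 3 and 4). The SAP itself separates these women when it studies bone loss. If the two histories lead to different changes after Week 52, that difference stays in the residual.

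At stake is the width of the intervals from the only adjusted analysis of the named bone endpoint. Separately, the model fits a treatment term but the plan does not say that its estimate will be shown. Two per-group intervals do not give the interval for the difference.

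**Working it through.** **No BMD figure to reproduce.** The documents state no SD, scan error or power for BMD. Their one power figure (SAP 2.2) is for menstrual blood loss. It holds: 360/2 x 0.8 = 144 per arm, 60% versus 40%, two-sided 0.05, gives 92.8% against the stated minimum of 90%. It has no bearing on BMD, except that I borrow 144 per arm below, assuming the same 20% loss of scans.

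**Model (assumed).** In percent of mean BMD:
- Y0 = T + error (pivotal baseline)
- Y52 = T + D1 + error
- Y104 = T + D1 + D2 + error

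B is the between-woman SD of T, e the scan error SD, d the SD of each true change, and r the correlation of D1 and D2. Then:
- Var(Y0) = B² + e²; Var(Y52) = B² + d² + e²; Var(Y104) = B² + 2d² + 2rd² + e²
- Cov(Y0,Y52) = Cov(Y0,Y104) = B²; Cov(Y52,Y104) = B² + d² + rd²

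Residual variance given Week 52 only: V1 = Var(Y104) - Cov(Y52,Y104)²/Var(Y52).

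With pivotal baseline added: V2 = V1 - [Cov(Y0,Y104) - Cov(Y0,Y52)Cov(Y52,Y104)/Var(Y52)]² / [Var(Y0) - Cov(Y0,Y52)²/Var(Y52)].

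Because Week 52 BMD is in the model, V1 and V2 are the same whether the response is Week 104 BMD or its absolute change.

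**Worked case: B = 12, e = 1.5, d = 2, r = 0.**
- V1 = 154.25 - 148²/150.25 = 8.466
- V2 = 8.466 - (144 - 144 x 148/150.25)²/(146.25 - 144²/150.25) = 8.466 - 2.156²/8.240 = 7.902
- Variance reduction: 1 - 7.902/8.466 = 6.7%. SE reduction: 1 - sqrt(7.902/8.466) = 3.4%
- 95% half-width of the difference, 1.96 x sqrt(2V/144): from 0.67 to 0.65 percentage points
- Equivalent sample size: 144 x 8.466/7.902 = 154, about 10 more women per arm

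**Grid.** B = 10, 12, 15; e = 1, 1.5, 2; d = 1.5, 2, 2.5 (27 combinations for each r).

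| r | Variance reduction, range | Median | Median SE reduction |
|---|---|---|---|
| +0.3 | 0.1 to 10.2% | 1.4% | 0.7% |
| 0 | 1.4 to 14.8% | 6.7% | 3.4% |
| -0.3 | 11.3 to 20.2% | 15.5% | 8.1% |

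A positive r (women who lost bone go on losing it) nearly cancels the gain. A negative r (women who lost more regain more) enlarges it. A second grid with B = 12 and different SDs for the two changes (1 to 3 before Week 52, 2 to 3 after, r from -0.3 to 0.3) gives SE reductions of 0 to 8.6%, median 3.0%.

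**Concurrent versus delayed E2/NETA.** Assume equal thirds from the three pivotal arms and a difference D in later change between the two relugolix arms. Leaving out the split adds (2/3) x D²/4 to the residual variance. With V1 = 8.466 and D = 0.5, 1 or 2 points, this adds 0.042, 0.167 or 0.667. Removing it lowers the SE by 0.2%, 1.0% or 3.7%.

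**Both additions.** In simulation (288 women, 3,000 runs for each of four settings, a simplified form of the SAP model) they lowered the SE by 1.7 to 7.7%. Bias was negligible with or without them.

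**The case against.** The strongest reply is that this is a preference among covariates, in a safety model on which no decision rests. BMD has no hypothesis test, no power claim and no place in the testing sequence. The strongest covariate, Week 52 BMD, is already in: on the grid above it explains 88 to 98% of the variance of Week 104 BMD. The bone history is described at length elsewhere in the SAP, and moving a half-width from 0.67 to 0.65 would not change how bone safety is read. All of that stands, and it limits the point to a minor one.

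Several stronger readings are tempting, and the documents do not support them.
- A reader might infer that the model ignores the pivotal arm. It does not. The pivotal period was 24 weeks and the extension 28, so 28 weeks of exposure means pivotal placebo and 52 weeks means either relugolix arm. Only the split within the 52-week level is missing.
- A reader might take this ANCOVA for the main bone-safety estimate. The protocol's declared summary is the unadjusted mean percent change with 95% CI per group, and the SAP gives that as well.
- A reader might suspect bias from chance imbalance in delayed add-back. With one third of women from that arm (assumed), the 95% range of imbalance is 1.96 x sqrt(2 x (1/3)(2/3)/144), about 11 percentage points. Multiplied by a 1-point difference in later change, that shifts the contrast by 0.11 points against a half-width of 0.67, and the confidence interval already allows for it.
- A reader might take the SAP's remark that the femoral neck is "prone to lower precision in the measurement" as evidence of large scan error in general. It concerns that one site.

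The reply does not remove the point. The gain was not negative anywhere on the grid, the data are already held, and the unreported treatment contrast does not depend on any assumed value.

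**Conclusion.** The point holds as a minor improvement to precision, not as an error. Treatment is randomized and the Week 52 value is adjusted for, so validity is not in question. The likely gain from pivotal-baseline BMD is a few percent of the standard error: about 1%, 3% or 8% at the median, depending on whether true changes before and after Week 52 correlate +0.3, 0 or -0.3. No document supplies that correlation, the between-woman SD or the scan error, so the range cannot be narrowed from the plan. The E2/NETA split adds less unless later change differs by around 2 points between the two pivotal relugolix arms. The missing between-group difference is a reporting gap whatever these values are.

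**What to change.** In SAP 9.3.3.1, for both the Week 104 and the Week 104/EOT model:
1. Add pivotal study baseline BMD at the same anatomical site as a covariate.
2. Replace the 28 versus 52 week factor by the three-level pivotal treatment group (relugolix + E2/NETA, relugolix + delayed E2/NETA, placebo), which contains it.
3. Report the LS mean difference between treatment groups with its 95% CI beside the per-group LS means. State that placebo patients who relapsed may have received open-label retreatment before Week 104, so the difference is not one between continuous treatment and 52 weeks off treatment.

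The cost is SAP wording before unblinding and two model degrees of freedom, one for the added covariate and one for the extra factor level. No new data are needed. Women without a pivotal-baseline scan would drop out of the adjusted model unless a simple rule keeps them in, for example a missing-value indicator with a fixed fill-in value. That rule should be written down in advance.

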ECGs (12-lead) will be obtained at Week 52/Baseline visit in this study, as well as if needed to evaluate any signs or symptom that require an ECG to assess. ECGs will be measured using standardized equipment provided by central core laboratory with the patient in a semi-supine or supine position after 5 minutes of rest. The ECGs will be assessed by central review and a report provided to the site. The investigator or sub-investigator (or a qualified individual at the investigational site) will interpret the ECG report provided by the central reviewer using one of the following categories: normal or abnormal. The investigator or sub-investigator will judge if any of the findings are clinically significant. Any ECGs performed after the Week 52/Baseline visit will be read locally.

6.5.2.6. **Bone Mineral Density**

Bone mineral density is determined using DXA scanning and will be assessed at the lumbar spine (L1, L2, L3, and L4), total hip, and femoral neck (same leg within each patient). Training, quality review, and readings will be done by a central radiology laboratory as described in the central radiology charter for bone mineral density.

Throughout the study, the same DXA apparatus will be used at each site and operated in the same scan mode for all scans for each patient. This should be the same as used for the patient during the OLE study. A central core imaging laboratory will collect and evaluate all DXA scans for acceptability and will have bone mineral density assessed as per the imaging charter. Data from the DXA scans will be managed and analyzed separately by the core laboratory and integrated into the study's database at the end of the study. Bone mineral density changes for individual subjects will be monitored by a central radiology laboratory over the course of the study.

Patients who experience a bone mineral density loss of $\geq 7\%$ from the Parent study baseline at any of the anatomical sites assessed will be discontinued from the study and will undergo another bone densitometry scan as described below. Patients should be assessed for secondary causes of bone loss and followed-up further if not improving on 6 months follow-up scan unless an alternative etiology has been identified.

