Clinical laboratory data consist of chemistry, hematology, and hormonal tests. Only data collected by the central laboratory will be used to do the analyses.

The incidence of vasomotor symptoms as assessed through adverse event reporting will be summarized by the study treatment arm.

Bone mineral density data will be collected and analyzed by the central radiology laboratory including bone mineral content (g), bone area (area, cm²), and bone mineral density (g/cm²) each for L1, L2, L3, L4, total hip, and femoral neck, and average bone mineral density of L1-L4 (lumbar spine), Z-score for bone mineral density lumbar spine (L1-L4), total hip, and femoral neck.

All BMD data will be listed and summarized by visit. The change, percent change from study Week 52/Baseline to Weeks 76 and 104 and associated 95% CIs will be presented by the study treatment group for each bone mineral density parameter. The number and percentage of patients meeting a bone mineral density decline of at least 3%, 4%, 5%, 6%, or 7% by body area (lumbar spine, total hip, or femoral neck) will be estimated with 95% CIs by the study treatment group.

Additional analyses will be performed to exam the correlation between bone mineral density loss with demographic and baseline characteristics and with treatment exposure. Details will be provided in the SAP.

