3.3. Safety Follow-Up Analyses

Patients who experience a BMD loss of $\geq 7\%$ from the pivotal study baseline at any of the anatomical sites assessed will be discontinued from the study and will undergo another bone densitometry scan as described below. Patients with a BMD loss of $\geq 7\%$ at lumbar spine, total hip, or femoral neck at their Week 104/Early Termination visit relative to pivotal study baseline measurement will undergo another bone densitometry scan at 6 (± 1) months after the last dose of study drug and will be contacted to obtain information about medications and conditions (eg, pregnancy) that might affect BMD through the time of the follow-up bone densitometry scan. Patients should be assessed for secondary causes of bone loss and followed-up further if the 6-month follow-up scan does not show improvement, unless an alternative etiology has been identified. The follow-up bone densitometry scan will be submitted for central reading.

Patients whose menses have not resumed as of the safety follow-up visit and for whom there is no explanation for the lack of resumption (eg, medical procedure or medications) will be contacted again by telephone 12 (± 2) weeks after the Safety Follow-up visit to determine if menses have resumed.

Complete data collected during the additional safety follow-up period will be summarized and reported in an addendum to the CSR.

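### The SAP's BMD bands replace the Protocol 9.5 decline counts, so the planned tables lose the 4, 6 and 7% counts and only bracket the 7% count

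*SAP*

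**What the plan says.** Protocol 9.5 plans cumulative threshold counts at three sites (femoral neck, total hip and lumbar spine): "The number and percentage of patients meeting a bone mineral density decline of at least 3%, 4%, 5%, 6%, or 7% by body area". Each count comes with a 95% CI for each study treatment group. The protocol sentence names no reference baseline. The sentence before it concerns change from Week 52/Baseline.

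SAP 9.3.3.1 has a different table: "Categorical representation of percentage change from Week 52/Baseline to Week 104 (also Week 104/EOT) will be presented by the number and proportion of patients" with an increase, no change, or a decline of up to 2%, over 2 to 3%, over 3 to 5%, over 5 to 8%, or over 8%. It is broken down by pivotal study treatment group, not by the groups randomized in this trial. SAP 9.3.3.2 applies the same bands to the other reference point: "Categorical representation of percentage change from pivotal study baseline to all the timepoints" at which BMD was scheduled, by treatment group and by the six treatment sequences of SAP Table 20.

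The 7% figure comes from the trial's own bone rule. Under Protocol 6.5.2.6, women who lose 7% or more "from the Parent study baseline at any of the anatomical sites assessed will be discontinued from the study". Those at 7% or more at Week 104/Early Termination, relative to Parent baseline, have another scan at 6 (±1) months. SAP 3.3 repeats both parts. Footnote p of Protocol Table 1-1 has the follow-up scan triggered by a loss of more than 7%.

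**The concern.** The SAP states that it is based on Amendment 1, and Amendment 1 contains the threshold counts. The BMD sections do not say that the counts were dropped or why.

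Change in BMD is a named safety topic in a trial that takes exposure up to 104 weeks. A reader of the study report will want to know how many women in each group, at each site, lost as much bone as the trial itself treats as needing follow-up. In the planned tables, women who lost 7 to 8% are merged with those who lost 5 to 7%.

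The handling is also uneven. Protocol 4.5 pairs two bone criteria for removal from therapy: a Z-score below -2.0, or a decrease of at least 7% from Parent baseline. SAP 9.3.3.1 and 9.3.3.2 tabulate the first exactly and the second not at all.

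**Working it through.** The plan gives no figure to reproduce. The check is whether each protocol count can be rebuilt from the SAP bands.

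**Inputs.** Protocol 9.5 thresholds: 3, 4, 5, 6, 7% (each meaning at least). SAP 9.3.3.1 and 9.3.3.2 band edges for declines: 0, 2, 3, 5, 8% (each band open below and closed above).

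**Rule.** Let N(>c) be the number of women with a decline above c%, obtained by adding bands. If threshold k is a band edge, N(≥k) equals N(>k) plus any exact ties. If k lies inside a band, the table gives only N(>next higher edge) ≤ N(≥k) ≤ N(>next lower edge).

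| Threshold | Position | What the SAP table gives |
|---|---|---|
| 3% | edge | N(>3), ties at exactly 3% excluded |
| 4% | inside over 3 to 5 | N(>5) to N(>3) |
| 5% | edge | N(>5), ties at exactly 5% excluded |
| 6% | inside over 5 to 8 | N(>8) to N(>5) |
| 7% | inside over 5 to 8 | N(>8) to N(>5) |

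Three of the five protocol counts are lost, on both baselines.

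**How wide is the 7% bracket?** The documents give no mean or SD for BMD change, so the following are assumptions for illustration. With percent change normal, mean m and SD s, the proportion with a decline of at least c is Φ((−c − m)/s). For m = −1, s = 3: at 7%, Φ(−2.00) = 2.3%; at 5%, Φ(−1.33) = 9.1%; at 8%, Φ(−2.33) = 1.0%.

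| Assumed mean, SD | At least 7% | Lower bound (over 8%) | Upper bound (over 5%) |
|---|---|---|---|
| −1%, 3% | 2.3% | 1.0% | 9.1% |
| −1%, 4% | 6.7% | 4.0% | 15.9% |
| −2%, 4% | 10.6% | 6.7% | 22.7% |
| −3%, 4% | 15.9% | 10.6% | 30.9% |

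Over these cases the upper bound is about 1.9 to 4.0 times the true proportion (30.85/15.87 and 9.12/2.28).

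**Does another planned output supply the count?**

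- SAP 5.1 tabulates reasons for discontinuation, not size of BMD loss.
- The closing text of SAP 9.3.3.3 lists post-treatment follow-up scans. It also calls for a scan in women who stopped treatment early after Week 60, so the listing is not confined to the 7% group.
- SAP 3.3 says follow-up data will be summarized in an addendum; SAP 9.3.3.3 makes this optional. Neither specifies a 7% count.
- The overall BMD categories in 9.3.3.1 and 9.3.3.2 cover lumbar spine and total hip only. The 7% rule also covers femoral neck.

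**The case against.** The best defence is that little is lost. The BMD safety endpoint in the protocol, percent change from Week 52/Baseline to Week 104 at three sites, is kept with CIs. The SAP adds an ANCOVA, pivotal-baseline analyses by treatment sequence, and Z-score counts. Protocol 9 leaves detailed methods to the SAP, and the SAP says its methods are consistent with the earlier phase 3 studies. The bands may therefore have been harmonised with those studies; their SAPs are not among these documents, so this cannot be checked. This stands as a possible explanation, but it does not explain omitting rows that could sit in the same table.

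A reader might also infer three stronger things, and the documents do not support them:

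- *That the trial cannot report its 7% count.* Only the planned tables cannot. The continuous data are collected, Protocol 9.5 says all BMD data will be listed, and women at the threshold at the last visit are identified operationally for the follow-up scan.
- *That the protocol promised a count of 7% declines from Parent baseline and the SAP withdrew it.* The Protocol 9.5 sentence states no baseline and follows one about Week 52/Baseline. The 7% rule uses Parent baseline. The protocol does promise counts by body area; it does not clearly promise that one, and it does not mention an any-site count.
- *That a live stopping rule goes unmonitored.* Scheduled DXA occurs only at Week 52/Baseline and Week 104/Early Termination, and the removal criterion in Protocol 4.5 refers to the Week 52 scan of the extension study. During this trial the 7% level mainly triggers the follow-up scan.

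**Conclusion.** The SAP replaces a protocol-stated descriptive safety analysis with one that is not equivalent, and gives no reason. Three of five threshold counts (4, 6 and 7%) cannot be obtained from the planned tables. The 3% and 5% counts can, apart from exact ties. For 7% the tables give only N(>8%) to N(>5%). That conclusion follows from the cut-points alone; only the illustrated widths rest on assumed means and SDs.

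The gap matters most in SAP 9.3.3.2, because the follow-up rule is defined on the pivotal (Parent) baseline. This is a shortfall in prespecified descriptive reporting. No estimate, test, alpha level, power figure or primary-endpoint result changes.

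**What to change.** Keep the SAP bands and add to them:

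1. **SAP 9.3.3.1:** cumulative rows for declines of at least 3, 4, 5, 6 and 7% with 95% CIs, by anatomical site and by randomized-withdrawal treatment group. Correct or justify the present breakdown by pivotal study treatment group.
2. **SAP 9.3.3.2:** the same rows, by the six combined groups of Table 20 and by the two randomized groups.
3. **SAP 9.3.3.2:** one further row for a decline of at least 7% from pivotal baseline at any of the three sites at Week 104/EOT. This goes beyond Protocol 9.5 and is suggested because it matches the follow-up rule.
4. State the reference baseline for each set of rows, since Protocol 9.5 does not.
5. Reconcile footnote p of Protocol Table 1-1 (more than 7%) with Protocol 6.5.2.6 (7% or more), and the firm follow-up summary in SAP 3.3 with the optional one in SAP 9.3.3.3.

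The cost is a few descriptive table rows from data already collected.
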